8.4.2 Operating Characteristics

To assure safety in this Phase II trial, the operating characteristics of the above-defined escalation rule have been determined. The operating characteristics denote the probability of escalation to the next SBRT fraction dose level, for a *true* DLT rate at the current dose level. For a true DLT rate that is high, we desire the probability of escalation to be low. As noted in the table below, the probability of escalating beyond a certain dose level, if that dose level truly has e.g. a 40% DLT rate, is 0.23.

Operating characteristics of the escalation rule									
	True DLT rate at a particular dose level								
Probability of escalating	10%	20%	30%	40%	50%	60%	70%	80%	90%
	0.89	0.66	0.42	0.23	0.11	0.04	0.01	0.002	<0.001

8.4.3 Assessment of Late Toxicity

Late toxicity is defined as an adverse event which occurs beyond 30 days from last injection of ipilimumab, as detailed in Section 5.2. Adverse events which are observed months after treatment will be recorded. We will monitor for both immune-related and SBRT-related events as described in Section 5.2.

8.5 Plans for Data Analysis

Toxicity: Any patient who receives any amount of radiation or study medication will be analyzed for toxicity. All dose-limiting toxicities and late toxicities will be graded and tabled by lesion site

CONFIDENTIAL

This material is the property of the study sponsor. Do not disclose or use except as authorized in writing by the study sponsor

Printed on 1/31/2017

stratum and SBRT fraction dose level. Toxicity attribution to either SBRT or ipilimumab will be described if possible.

Response: Clinical response at a non-index lesion will be scored using the immune-related response criteria (irRC) referred to as irRECIST 1.1 and discussed by others.(25,26) The index lesion will not be included in measuring response. The number of immune-related responses will be tabled by stratum and SBRT fraction dose level. **At the MTD**, the immune-related response rate and 95% exact CI will be estimated separately for previously untreated and previously treated metastatic patients and will inform our decision-making. The table below displays 95% exact CIs for selected numbers of responses.

95% Exact Confidence Interval for Event Rate based on 14 patients in each stratum at the Maximum Tolerated SBRT Fraction					
No. of Events	%	95% exact CI	No. of Events	%	95% exact CI
2	14.3	1.8 – 42.8	10	71.4	41.9 – 91.6
4	28.6	8.4 – 58.1	12	85.7	57.2 – 98.2
6	42.9	17.7 – 71.1	14	100.0	80.7*
8	57.1	28.9 – 82.3	* lower bound of 95% 1-sided CI		

Immune-related progression-free and overall survival will be estimated by the Kaplan-Meier method separately for previously untreated and previously treated metastatic patients who were treated at the MTD. The estimated 6 month irPFS and 12 month OS rates and 95% CIs will inform our decision-making, as they are considered by many to be better measures of clinical benefit. Interestingly, PFS6 and OS12 rates were approximately 25% and 45%, respectively, in 137 previously treated metastatic melanoma patients treated with ipilimumab alone.(3) Evaluation using historical benchmarks has been proposed by Korn et. al. for Phase II decision-making in metastatic melanoma (27).

Immunologic Endpoints: For measures of lymphocyte activation, outcomes will first be described using plots and descriptive statistics. Natural log transformation may be applied, as necessary, prior to statistical comparison. Within-patient differences (e.g., baseline vs. post-treatment) will be examined by Student's t test for paired data or nonparametric Wilcoxon signed ranks test. For lymphocyte analyses, outcomes will first be described using plots and descriptive statistics. For T cell response, the number of immune responses (>2 fold pre/post increase) will be tabled by fraction dose level. The overall immune response rate and 95% exact CI will be estimated separately for previously untreated and previously treated metastatic patients treated at the MTD.

With several post-treatment samples intended, trends over time may be investigated by repeated measures ANOVA (if data are complete). Alternatively, mixed effects models will describe trends in individual APC and T cell outcomes measured during immunotherapy, including drug doses as fixed effects. Although the number of subjects is modest, serial blood measures for immune monitoring are intended. (Thus, longitudinal modeling may be successful. We will attempt to extend this investigation to longitudinal methods for multivariate data with the goal of modeling jointly the inter-dependency among several longitudinal outcomes. For example, a joint analysis may determine how the association between the induction of CD86 on APCs and antigen-specific T cells evolves over time. Because the number of immunologic outcomes to be modeled jointly will be small (several at most), we will attempt to use the pairwise model fitting approach for maximum likelihood estimation as previously described.(27)

CONFIDENTIAL

This material is the property of the study sponsor. Do not disclose or use except as authorized in writing by the study sponsor

Printed on 1/31/2017

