RADVAX: A STRATIFIED PHASE II DOSE ESCALATION TRIAL OF STEREOTACTIC BODY RADIOTHERAPY FOLLOWED BY IPILIMUMAB IN METASTATIC MELANOMA

Principal Investigator: [name] MD PhD
University of Washington
Department of Radiation Oncology
[contact]
[contact]
Email: [contact]

Funding Sponsor: Department of Radiation Oncology
University of Washington

Sub-Investigators [name]
[name]
[name]
[name]

Statistician: [name]

Version date: *Protocol Amendment 7: version November 15, 2016
(replacing Protocol Amendment 6: version January 15, 2016)*

CONFIDENTIAL

This material is the property of the sponsor. Do not disclose or use except as authorized in writing by the study sponsor

Printed on 1/31/2017

Table of Contents

STUDY SUMMARY 1

1 INTRODUCTION 2

2 STUDY OBJECTIVES 4

3 STUDY DESIGN..... 4

4 SUBJECT SELECTION AND WITHDRAWAL 6

5 STUDY DRUG..... 7

6 STUDY PROCEDURES 7

7 ASSESSMENT OF TUMOR REPOSE..... 12

8 STATISTICAL PLAN 144

9 SAFETY ASSESSMENT AND ADVERSE EVENT REPORTING 18

10 REGULATORY, QUALITY AND ADMINISTRATIVE REQUIREMENTS..... 22

REFERENCES 23

List of Abbreviations

SBRT: Stereotactic body radiation therapy
 CTLA 4: Cytotoxic t-lymphocyte antigen 4

Study Summary

Title	RADVAX: A STRATIFIED PHASE II DOSE ESCALATION TRIAL OF STEREOTACTIC BODY RADIOTHERAPY FOLLOWED BY IPIILIMUMAB IN METASTATIC MELANOMA
Short Title	RADVAX
Protocol Number	CC IRB # 9031
Phase	Phase II
Methodology	Open Label
Study Duration	3 years
Objectives	
 1. The primary objectives are to determine feasibility and immune-related clinical responses associated with SBRT when given in conjunction with ipilimumab 2. The secondary objectives are to determine late toxicity and immune pharmacodynamic changes after SBRT followed by ipilimumab
Number of Subjects	40
Diagnosis and Main Inclusion Criteria	Patients with previously untreated or previously treated metastatic melanoma with bone, lung, liver, or subcutaneous or nodal involvement but without evidence of active brain involvement. Patients who have previously been treated with radiation will be included in the study, so long as a suitable plan for treatment can be developed.
Study Product, Dose, Route, Regimen	Stereotactic Body Radiation Therapy
Duration of administration	Radiation Treatment to be delivered prior to initiation of ipilimumab
Reference therapy	Ipilimumab

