3.2 Primary Study Endpoints

Late toxicity is defined generally as an adverse event associated with the treatment which occurs beyond 30 days after last injection of ipilimumab (i.e., adverse events which are observed months after treatment are most likely associated with SBRT) and is defined more precisely in Section 5.2.

Clinical response will be scored on a non-index lesion or lesions using immune-related response criteria (irRC). Immune-related progression-free survival (irPFS) is defined as the time from first day of radiotherapy to first documented irPD, death due to any cause or last patient contact alive. Immune pharmacodynamic changes will be examined, as described in Section 7.22.(25) Overall immune response is defined as >2-fold pre-treatment/post-treatment increase in any of the key T cell parameters.

CONFIDENTIAL

This material is the property of the study sponsor. Do not disclose or use except as authorized in writing by the study sponsor

Printed on 1/31/2017

4 Subject Selection and Withdrawal

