4.1 Inclusion Criteria

- Patient ≥ 18 years old
- Histologically confirmed diagnosis of melanoma
- Previously treated or previously untreated stage IV melanoma by AJCC staging criteria
- Presence of an index lesion between 1 and 5 cm
- ECOG Performance status 0, 1, or 2
- Signed informed consent document
- Adequate renal, hepatic, and hematologic indices for ipilimumab therapy
- Ability to tolerate stereotactic body radiation therapy (e.g. lie flat and hold position for treatment)

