8.1 Design

This is a stratified Phase II study of escalating fractions of stereotactic body *radiotherapy* (SBRT) combined with immunotherapy for previously untreated or previously treated metastatic melanoma patients. Patients will undergo a short course of high dose SBRT to a single index lesion that is suitable for SBRT. These fractions will be administered several days apart. Radiotherapy will be immediately followed by ipilimumab, at the FDA-approved dose and schedule.

Stratified Phase II study: With safety data from an identical University of Pennsylvania study, SBRT fractions of two and three fractions has been shown to be safe. At UW/SCCA the Phase II study begins with Dose Level 1. If three fractions of SBRT are found to not be safe, the dose level will be reduced to Dose level -1 for the phase II portion of that stratum.

Stratification by Site of Index Lesion						
Dose Level	Stratum 1: bone or lung			Stratum 2: liver or subcutaneous		
	Dose per fraction	Fractions	# Patients	Dose per fraction	Fractions	# Patients
-1	8 Gy	2	6	6 Gy	2	6
1	8 Gy	3	6	6 Gy	3	6

The MTD has been defined by the Phase I trial at the University of Pennsylvania as 3 fractions of SBRT. The Phase II study can commence at UW/SCCA at dose level 1 (above). Patients will be treated at the MTD defined for their index lesion site. In Phase II, patients will be stratified by disease site: Stratum 1: phase 1 bone or lung and Stratum 2: phase 1 liver or subcutaneous. Stratum-specific response rates will be calculated. Enrollment will proceed independently for the

CONFIDENTIAL

This material is the property of the study sponsor. Do not disclose or use except as authorized in writing by the study sponsor

Printed on 1/31/2017

two strata. Forty total patients will be enrolled in this phase. Thus a maximum of 40 patients will be entered at the MTD. Twenty patients will be enrolled in each stratum

8.2 Objectives:

Phase II study: The primary objectives are to determine for each stratum, immune-related clinical response rate, immune-related progression-free survival rate at 6 months (irPFS6), and overall survival rate at 12 months (OS12). The secondary objectives are to gather additional data on acute and late toxicity and immune pharmacodynamic changes.

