8.3 Endpoints

Toxicity: CTCAE version 4.0 grades will be employed. Any patient who receives any amount of radiotherapy or study medication will be included in the toxicity analysis.

Dose-limiting toxicity (DLT) is defined generally as associated with the treatment, and for ipilimumab, that the event must be consistent with an immune-related effect. DLT is experienced during study treatment or within 30 days after last injection of ipilimumab, as long as the patient has not started another systemic treatment for cancer and is defined more precisely in Section 5.2.

Maximum tolerated SBRT fraction (MTD) is defined as the SBRT fraction dose level at which 0-1/6 patients experience DLT and at least 2 patients treated at the next higher dose level experience DLT (or the apparent MTD is Dose level 1).

Late toxicity is defined generally as an adverse event associated with the treatment which occurs beyond 30 days after last injection (i.e., adverse events which are observed months after treatment are most likely associated with SBRT) and is defined more precisely in Section 5.2.

Response: Immune-related clinical response will be scored on a non-index lesion using immune-related response criteria (irRC) according to irRECIST 1.1 (48). Patients who do not complete a clinical response evaluation, with the exception of those patients with rapidly progressing disease, will be scored as unevaluable. The immune-related clinical response rate is defined as the proportion of patients treated at the MTD who achieve either a complete or partial immune-related response. Unevaluable patients are included in denominator for the calculation of the objective response rate.

Immunologic outcomes include: 1) analysis of lymphocyte subsets and lymphocyte activation, 2) analysis of antigen-specific T cells and 3) tumor-specific T cells, as described in Section 7.2.2. For T cell response analyses, overall immune response is defined as >2 fold pre-treatment/post-treatment increase in any of the key T cell parameters.

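### Response is scored only outside the index lesion, but no entry criterion requires disease there, so the all-treated response rate can be biased downward by a small, unknown amount

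*Combined protocol and SAP*

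**What the plan says.** Section 8.2 puts response first among the Phase II aims: "The primary objectives are to determine for each stratum, immune-related clinical response rate". Three sections restrict where response is measured. Section 3.2 states "Clinical response will be scored on a non-index lesion or lesions", 8.3 likewise scores a non-index lesion, and 8.5 is categorical: "The index lesion will not be included in measuring response".

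Section 8.3 defines the rate as "the proportion of patients treated at the MTD who achieve either a complete or partial immune-related response" and adds "Unevaluable patients are included in denominator for the calculation of the objective response rate".

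The only lesion-level entry line in 4.1 is "Presence of an index lesion between 1 and 5 cm". The stage IV criterion gives no minimum number of lesions, and 4.2 says nothing about disease outside the index lesion. The Study Summary asks for "metastatic melanoma with bone, lung, liver, or subcutaneous or nodal involvement but without evidence of active brain involvement", which a single metastasis can satisfy. Baseline imaging is required in 6.4 and in the Eligibility/Pre-Treatment column of 6.5, but neither says that the scan must show a non-index lesion.

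**The concern.** The entry criteria and the endpoint do not match. The endpoint asks whether irradiating one lesion, followed by ipilimumab, leads to response elsewhere. That can be answered only in patients who have disease elsewhere, and the plan does not select for it.

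A patient whose single metastasis serves as the index lesion passes every listed criterion. Such a patient has nothing that 8.3 and 8.5 allow to be scored as a response, yet is one of the patients treated at the MTD. Each one lowers a primary rate whatever the treatment does. Section 8.5 says the rate will guide decision-making, and 8.6 sets it in the context of a 10.9% rate for ipilimumab alone, so a downward bias matters for how the result is read.

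**Working it through.** **Inputs.** Planned size is 20 per stratum (8.1). The 8.6 statement uses a 20% response rate and 14 per stratum. The 8.5 precision table also uses 14. The number k of patients with no disease outside the index lesion is not given; k = 1 to 4 of 20 is assumed.

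**The plan's own figure.** P(no responses in 14) = (1 − 0.20)^14 = 0.044, which agrees with the <0.05 in 8.6.

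**Dilution of the rate.** Take 20% as the rate among assessable patients. The expected all-treated rate is 0.20 × (20 − k)/20. The last column shows what the assessable-set rate would be if 4 responses were observed, with the exact (Clopper-Pearson) 95% CI.

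| k of 20 | Expected responses | Expected all-treated rate | 4 responses, assessable set |
|---|---|---|---|
| 0 | 4.0 | 20% | 4/20 = 20.0% (5.7–43.7) |
| 1 | 3.8 | 19% | 4/19 = 21.1% (6.1–45.6) |
| 2 | 3.6 | 18% | 4/18 = 22.2% (6.4–47.6) |
| 3 | 3.4 | 17% | 4/17 = 23.5% (6.8–49.9) |
| 4 | 3.2 | 16% | 4/16 = 25.0% (7.3–52.4) |

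The loss is 0.2 to 0.8 expected responses per stratum.

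**Smaller groups.** Section 8.5 also estimates the rate separately by prior treatment, and the group sizes are not given. In a group of 10 (assumption), one such patient moves the expected rate from 20% to 0.20 × 9/10 = 18%. The exact CI for 2/10 is 2.5% to 55.6%.

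**Effect on the 8.6 statement.** This depends on what the 20% means.

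- If it is the rate among assessable patients, as in the table, one such patient in 14 gives 0.8^13 = 0.055, just above 0.05. With 20 per stratum and k = 4, it is 0.8^16 = 0.028.
- If it is the all-treated rate, as 8.3 defines the endpoint, the other 13 patients have rate 0.20 × 14/13 = 0.2154, and (1 − 0.2154)^13 = 0.043. The statement stands.

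These are two different scenarios, and their results should not be combined.

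**Distance from the benchmark.** To bring 20% down to 10.9% by dilution alone, the affected share would have to be 1 − 10.9/20 = 45.5%.

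**The case against.** **Section 7.1.1 is broader.** It describes overall response by RECIST 1.1, immune criteria and/or investigator-assessed clinical benefit, without excluding the index lesion. On that text alone, a patient with only an index lesion might be scored. But 8.3 and 8.5 are the specific endpoint and analysis rules, and 8.5 excludes the index lesion outright. The general wording does not override them.

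**The all-treated denominator is a deliberate, conservative choice.** This stands, and there is no reason to replace it. Feasibility is also a primary objective and needs no non-index disease, so broad entry can be defended. It does not make a patient with nothing to score informative about response elsewhere.

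**Unevaluable patients are already covered.** Section 8.3 says "Patients who do not complete a clinical response evaluation, with the exception of those patients with rapidly progressing disease, will be scored as unevaluable". A reader might infer a separate defect, that these patients have no label. The rule can reasonably be read to include them, and under any label the effect on the rate is that of a non-response, so a new label changes no result.

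**The number affected is hypothetical.** This also stands. Most patients with stage IV disease may have several lesions, in which case the effect is close to nil. The documents give no count either way.

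**Further inferences that the documents do not support.** A reader might conclude that the <0.05 in 8.6 is wrong. It fails only if the 20% is taken among assessable patients; on the 8.3 definition it holds. A reader might also extend the point to patients with non-measurable disease outside the index lesion. How those are scored depends on irRECIST 1.1, which the document does not reproduce, so the point is confined to patients with no other disease.

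**Conclusion.** The mismatch is real and follows from the text: scoring is off-index only, the denominator is everyone treated at the MTD, and nothing in 4.1, 4.2, the Study Summary, 6.4 or 6.5 requires disease outside the index lesion. The direction of the bias is certain, downward; its size is not known. With 1 to 4 affected patients of 20 and a 20% rate among assessable patients (both assumptions, the 20% borrowed from 8.6), the expected rate is 19% to 16%, well inside the sampling uncertainty of a stratum of 20.

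The consequence is limited. The response analysis is descriptive, no test against 10.9% is planned, and OS12 does not depend on which lesion is scored. A reader might infer that the response result would be unusable or that the historical comparison would be reversed. The figures do not support that: only an affected share near 45.5% would pull 20% down to the benchmark. The point is minor but worth correcting, because following the stated rules gives a biased answer to the question the endpoint asks.

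**What to change.** Add one line to 4.1: at least one non-index lesion assessable by irRECIST 1.1 on the baseline scan. Section 6.4 now places baseline imaging after the patient has been deemed eligible, while 6.5 lists it under Eligibility/Pre-Treatment. Align 6.4 with 6.5 so that the criterion is confirmed before the first SBRT fraction. That is a clearer anchor than enrolment, which 3.1 equates with consultation and 4.3 places after eligibility is established.

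For patients already treated, or if eligibility is left unchanged, keep the all-treated rate of 8.3. Beside it in 8.5, report the rate and exact 95% CI in patients with a non-index lesion on the baseline scan. Because that set is fixed before treatment, outcome cannot influence who belongs to it. It also gives a consistent reading across patients entered before and after an amendment.

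The cost is one eligibility line, an edit to 6.4 and one extra row in the response table, with no new procedure. The downside of the entry criterion is that a few patients with disease only in the index lesion become ineligible. That slightly slows accrual and slightly narrows the population for feasibility, irPFS6 and OS12. The supplementary rate alone avoids this.

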8.6 Sample Size/Power

If the Phase II study investigates both SBRT fraction dose levels for both strata, then a total of 40 patients will be enrolled on the study. There will be 40 patients enrolled at the Phase II dose. An objective response rate of 10.9% (by modified WHO criteria) was observed by Hodi et. al. in 137 previously treated metastatic melanoma patients treated with ipilimumab alone.(3) We anticipate that the combination of SBRT and ipilimumab will result greater efficacy for each stratum. If the true immune-related response rate is 20%, then the probability of observing no responses in 14 patients in either stratum, is <0.05.

With regard to statistical power, our preliminary clinical data on 16 patients treated on the single-infusion CD40 mAb trial indicate the mean difference \pm SD_{diff} between post- and pre-treatment percentages of CD19+ B cells expressing CD86 were: 17.1% \pm 11.1%, with effect size of 1.5 SD_{diff} units. By pooling over strata at the MTD, with a total of 28 patients enrolled, there is >80% power to detect a more modest effect size of $\frac{3}{4}$ SD_{diff} units, based on a paired t-test at 2-sided alpha level of 0.005 after adjusting for testing of multiple APC measures. Moreover, at the end of our current Phase I study of anti-CTLA-4 antibody (tremelimumab) and anti-CD40 antibody (CP-870,893) (UPCC 05609), we will evaluate pre/post differences in percentages of CD19+ B cells expressing CD86 and other relevant immune outcomes and we will update the power calculation for those effect sizes.

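### Section 8.2 makes irPFS6 and OS12 primary within each index-site stratum, but Section 8.5 estimates them only by prior-treatment status, and its response CI sentence does not match its own table

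*Combined protocol and SAP*

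**What the plan says.** Section 8.2 sets the Phase II objectives: "The primary objectives are to determine for each stratum, immune-related clinical response rate, immune-related progression-free survival rate at 6 months (irPFS6"), followed by the 12-month overall survival rate (OS12). Section 8.1 defines the strata by index-lesion site (bone or lung; liver or subcutaneous), says that "Twenty patients will be enrolled in each stratum", and adds that "Stratum-specific response rates will be calculated".

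Section 8.5 uses two groupings:

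- Response counts: "The number of immune-related responses will be tabled by stratum and SBRT fraction dose level".
- Response rate and interval, at the MTD: "the immune-related response rate and 95% exact CI will be estimated separately for previously untreated and previously treated metastatic patients". The table that follows is headed "95% Exact Confidence Interval for Event Rate based on 14 patients in each stratum at the Maximum Tolerated SBRT Fraction".
- Survival endpoints, at the MTD: "Immune-related progression-free and overall survival will be estimated by the Kaplan-Meier method separately for previously untreated and previously treated metastatic patients".

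Section 8.6 argues the sample size by stratum: "If the true immune-related response rate is 20%, then the probability of observing no responses in 14 patients in either stratum, is <0.05".

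**The concern.** The objective and the analysis refer to different populations. Prior treatment is an eligibility description in Section 4.1, where both kinds of patient may enter. It is not a stratification factor and has no quota or planned number. Section 8.5 itself uses the word stratum for lesion site when it describes the toxicity tables, so the word cannot be read as prior-treatment status.

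Three things are at stake.

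- **Missing primary estimates.** Followed as written, 8.5 yields no irPFS6 or OS12 for either site stratum.
- **Unfixed grouping.** Section 8.5 says these rates and their CIs will inform decisions. With 8.2 and 8.5 in conflict, the grouping to be emphasised could be settled after the results are known.
- **Unclear population.** Section 8.5 does not say whether prior-treatment groups are pooled over site or formed within each site. Section 8.6 does say that strata are pooled where it intends this, for the immune power calculation. The radiation regimen differs by site (Section 6.2.3), and Section 8.1 allows the dose level to be reduced in one stratum alone. A pooled prior-treatment estimate would therefore mix regimens, while a nested one would rest on small groups.

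**Working it through.** **Step 1. Compare the groupings.**

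| Quantity in 8.2 (each per site stratum) | Planned by site stratum? | Planned by prior treatment? |
|---|---|---|
| Response rate | Yes: rates in 8.1, counts in 8.5, CI table heading in 8.5 | Yes: the 8.5 sentence assigning rate and exact CI |
| irPFS6 | Not stated anywhere | Yes: 8.5, Kaplan-Meier |
| OS12 | Not stated anywhere | Yes: 8.5, Kaplan-Meier |

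The gap is complete for irPFS6 and OS12. For response it is confined to the sentence that assigns the CI.

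**Step 2. Reproduce the plan's figures.** Clopper-Pearson 95% limits for x events in n patients are the Beta(x, n−x+1) quantile at 0.025 and the Beta(x+1, n−x) quantile at 0.975. With n = 14:

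- 2/14: 1.8–42.8%
- 4/14: 8.4–58.1%
- 6/14: 17.7–71.1%
- 8/14: 28.9–82.3%
- 10/14: 41.9–91.6%
- 12/14: 57.2–98.2%
- 14/14, one-sided 95% lower bound: 0.05^(1/14) = 80.7%

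All seven entries agree with the table. For 8.6, P(no response | true rate 20%) = 0.8^14 = 0.044, consistent with the stated bound of 0.05 for a single stratum. Both calculations are for a group of 14 labelled as a site stratum. The plan gives no precision figure for a prior-treatment group.

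**Step 3. Apply the 8.6 argument to prior-treatment groups.** The formula is P(no response) = 0.8^n.

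| n | 0.8^n | Where it applies |
|---|---|---|
| 20 | 0.012 | site stratum at planned enrolment |
| 14 | 0.044 | the figure used in 8.6 |
| 13 | 0.055 | largest group size that exceeds 0.05 |
| 10 | 0.107 | largest possible size of the smaller group when 20 patients are split in two |

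- *Nested reading.* If n1 + n2 = 20, the smaller group has at most 10 patients, so the probability there is at least 0.107 whatever the split.
- *Pooled reading.* The probability exceeds 0.05 only in a group of 13 or fewer of the 40. The documents do not give the split.

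**Step 4. Precision of the survival rates.** Inputs are the benchmarks in 8.5 (about 25% for PFS6, about 45% for OS12). Assume the observed rates equal the benchmarks and no patient is censored before the landmark, so that Kaplan-Meier reduces to a proportion. For a site stratum of 20:

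- irPFS6: 5/20 = 25%, exact 95% CI 8.7–49.1%
- OS12: 9/20 = 45%, exact 95% CI 23.1–68.5%

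For prior-treatment groups, n must be assumed. Taking 10 to 30 patients and the approximate half-width 1.96·√(p(1−p)/n):

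- irPFS6 at 25%: ±26.8 points (n = 10) to ±15.5 points (n = 30)
- OS12 at 45%: ±30.8 points (n = 10) to ±17.8 points (n = 30)

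Precision in the groups that 8.5 names therefore depends on a case mix the design does not control.

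**The case against.** The strongest points on the other side are these.

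- **Primary status is not uniform across the document.** The Study Summary and Section 2 list feasibility and immune-related clinical response as primary. Section 3.2 includes irPFS without a 6-month rate and omits OS. This stands as a further inconsistency, so the claim here is limited to what 8.2 declares. Section 8.2 is the objectives statement of the statistical plan, and 8.5 does not analyse what it sets out.
- **The prior-treatment split has a reason.** The benchmarks come from previously treated patients given ipilimumab alone, and 8.5 uses the same split again for the immune response rate, so it looks deliberate. This is a good case for keeping the split, but it does not supply the missing site-stratum estimates.
- **A within-stratum reading is available.** The MTD is defined by index site, and 8.5 does not say that prior treatment replaces site. Even so, a nested analysis gives four subgroup estimates and no overall estimate for either stratum.
- **The study is descriptive.** No test, threshold or go/no-go rule attaches to irPFS6 or OS12, so no formal error rate is inflated. That is right, and the risk is selective emphasis. But where estimation is the primary analysis, the population being estimated has to be stated.
- **The no-response probabilities concern response, where the gap is smaller.** This is also right. They show that the plan's sample-size reasoning does not transfer to the other grouping. They do not measure harm to irPFS6 or OS12.

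**Conclusion.** The concern holds. Sections 8.2 and 8.5 conflict on the analysis population for irPFS6 and OS12, and no other section resolves it. Two of the three quantities that 8.2 makes primary have no stated analysis in the grouping that defines them. For response, the conflict is between one sentence in 8.5 and the heading of the table below it.

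The loss of the plan's stated assurance is certain only if the groups are nested within site. If they are pooled, it depends on a split that the documents do not give. The survival intervals in the working rest on benchmark rates and complete follow-up to the landmark; censoring would generally widen them. The conflict between the sections depends on none of these assumptions.

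This should be corrected before the analysis, but it does not call the design into question. Each patient's index site is known because it determines the radiation regimen, so the missing estimates can be produced from data already being collected.

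**What to change.** In Section 8.5:

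1. State that the immune-related response rate with exact 95% CI, and Kaplan-Meier irPFS6 and OS12 with 95% CIs, are estimated for each index-site stratum as the primary analysis.
2. Label the estimates by prior-treatment status as secondary, with the stated purpose of comparing previously treated patients with the ipilimumab-alone benchmark.
3. Say whether the prior-treatment groups are pooled over site or nested within it, and apply the same statement to the immune response rate.

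Amending 8.2 to define the objectives by prior treatment would also remove the contradiction. It fits the rest of the plan less well, because enrolment, radiation regimen, the CI table heading and the 8.6 argument are all organised by site.

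The cost is SAP wording and one further tabulation, with no extra patients, visits or data collection. The use of 14 per stratum in 8.5 and 8.6 against 20 in 8.1 is a separate matter, but could be corrected in the same revision.
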